## *2.2. Study visits pregnancy*

A broad risk evaluation will be performed in participating females at the initial contact (V1) including: evaluation of maternal age, parity, history of GDM in previous pregnancies, detailed family history, ethnicity, preconceptional diseases, obstetric history. Height (stadiometer measured to the nearest centimeter) and actual weight (calibrated scales, no clothes) will be additionally assessed. Moreover, an evaluation of preconceptional weight (self-reported) and BMI as well as measurement of blood pressure will be performed. All patients receive medical nutrition therapy (isocaloric diet containing 40-50% carbohydrates, 20% proteins and 30-35% fat, divided into three meals and three snacks) and lifestyle advice for 30 minutes following international recommendations and are advised on capillary blood glucose measurement (fasting as well as 1h after starting each meal) at the initial visit (V1). Randomisation will be done after a run-in period of 6 to 8 days (V2). The run-in period is omitted for patients who had a diagnosis of GDM before 24+0 according to the local guidelines and already received medical nutrition therapy, lifestyle intervention and advices on capillary blood glucose measurements. The third visit (V3) will be scheduled 8 to 10 days after V2 and further follow-up visits every two weeks (i.e. 12 to 16 days after each visit). HbA1c and glycosylated fibronectin, hsCRP, proBNP, Troponin T, will be assessed at V2 as well as at the first visit between 36+0 and 38+6 weeks of gestation (12 ml, non-fasting state) (V4). Detailed fetal ultrasound examinations, a detailed examination of dietary intake as well as a blinded CGM (control group only) will be performed at V2 and V4. Body weight change and use of glucose lowering medications (amount of insulin units) will be examined at every visit. At every follow-up visit glucose measurements (SMBG or rt-CGM) and routine ultrasound examinations (fetal biometry and umbilical artery doppler) will be evaluated by the medical staff and all patients will be treated according to the standard of care for patients with GDM. This includes lifestyle modification and insulin therapy if recommended thresholds are exceeded. Both groups will be treated to be in the target range between 65 to 140 mg/dl [3.6 to 7.8 mmol/l] with at least 8h fasting glucose levels equal or below 95 mg/dl [5.3 mmol/l] and 1h postprandial glucose

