### *2.3 Study visits postpartum*

Cord blood will be sampled and stored (at  $-80^{\circ}\text{C}$ ) immediately after delivery (VPP0). A postpartum examination will be scheduled within 48 hours after delivery (VPP1) for assessment of neonatal parameters and maternal HbA1c and glycosylated fibronectin, hsCRP, proBNP, Troponin T, (12 ml, non-fasting state), as well as between **8 weeks and 12 months** after delivery (VPP2) in all patients for a detailed re-examination of glucose homeostasis at postpartum (including lifestyle and dietary pattern as well as HbA1c, glycosylated Fibronectin, hsCRP, proBNP, Troponin T, as well as a blinded CGM for 10 days and an OGTT to assess the presence of prediabetic conditions after pregnancy with GDM). The postpartum OGTT is further used to provide estimates of insulin sensitivity,  $\beta$ -cell function and hepatic insulin extraction, the major physiological components of impaired glucose tolerance.

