### *2.4. Randomisation*

Participants will be randomized to either treatment (rt-CGM augmented glucose monitoring) or control group (routine care SMBG) in a 1:1 ratio. The minimisation method with a 0.85 assignment probability will be used to minimize the imbalance between the groups according to week of gestation at study entry i.e. at V1 (three strata: 24+0 to 25+6, 26+0 to 27+6, 28+0 to 29+6, 30+0 to 31+6), previous pregnancy with GDM (two strata: yes or no) and preconceptional overweight/obesity status with three strata: i. normal weight (i.e. BMI below  $25.0 \text{ kg/m}^2$ ); ii. overweight ( $\text{BMI } 25.0 - 29.9 \text{ kg/m}^2$ ); iii. obesity ( $\text{BMI equal or above } 30.0 \text{ kg/m}^2$ ). Randomisation will be performed at the second study visit (V2) by using the "MUW Randomizer" software.

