## *2.5. Intervention*

Patients randomized to the intervention group will be equipped with a rt-CGM sensor (Dexcom G6 sensor, a small flexible device that records interstitial glucose levels every five minutes) at V2. The sensor will be inserted into the subcutaneous tissue of the anterior abdomen wall (if this location is not tolerated by the pregnant patients, the upper buttock or posterior upper arm may be used instead). Additionally, patients will be advised to record capillary blood glucose values if glucose alerts or readings do not match with symptoms or expectations. Participants will be educated how to exchange the sensor (has to be exchanged every ten days) and will be equipped with a real-time CGM monitor and instructed in its use. The monitor provides the user with information about current glucose levels and notifies the patient before she reaches her upper or lower glucose threshold and when glucose levels change rapidly. All patients in the intervention group will specifically trained how to use the system. As an alternative to the real-time monitor the patients' smart phone with an anonymized access to the CLARITY® mobile app can be used (details see below: "Intervention: Device description").

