#### *2.10. Fetal biometry*

Parameters of fetal anthropometry as determined by ultrasound as well as neonatal data including length, weight, gestational age at delivery will be included in the final analysis. A detailed fetal ultrasound examination will be performed at V2 and repeated at V4 (between 36+0 to 38+6 weeks of gestation) to assess fetal growth parameters including head circumference, biparietal diameter and abdominal circumference and abdominal fat thickness,

femur length (measured and expressed as standardized gestational age related fetal growth percentiles ), amnion fluid index as well as size and location of the placenta and fetal subcutaneous tissue thickness. Moreover, fetal growth symmetry will be assessed by fetal head to abdomen circumference ratio and fetal doppler measurements (mainly umbilical artery and middle cerebral artery and ductus venosus). Furthermore, fetal hepatic size (all hepatic diameters, such as area and volume) and umbilical venous volume flow and an echocardiatic examination of the fetus will be performed in a subgroup (only study site Vienna).

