#### 3.2. Analysis plan

Analyses should be conducted on the intention-to-treat principle. Categorical variables will be summarized by counts and proportions; continuous variables data will be summarized by means and standard deviations (SD) or by median and interquartile range in the case of strong deviations from the normal distribution. Pearson's chi-square test will be used to compare differences in the primary outcome (difference in proportion of LGA newborns) and for binary secondary outcomes (such as caesarean section rate, shoulder dystocia and neonatal hypoglycaemia). Bernard's test will be used as an alternative if an expected frequency in contingency tables is equal or less than 5 and the Cochran-Mantel-Haenszel method will be used as sensitivity analysis to adjust for possible center specific effects. Continuous secondary outcome parameters (such as mean glucose, duration and amount of hyperglycaemia, glycaemic variability and other CGM measures, postpartum OGTT data, HbA1c, glycosylated fibronectin, hsCRP, proBNP, Troponin T, or anthropometric data of the newborn) will be compared by student's t-test. Rank based inference (such as the Brunner-Munzel test) will be used as an alternative in case of skewed distributed parameters. The association between HbA1c, CGM measures and delivery and risk of LGA offspring will be assessed by binary logistic regression. There are many possible objectives for which analysis could be performed in this study (e.g. functional principal components analysis for CGM data). Hence, the present analysis plan represents only a selection of methods, which will be used for analysing the main objectives. Risk and time preferences will be analysed by non-parametric and parametric methods. In particular, we plan to fit the choice data to a CRRA (constant relative risk aversion) utility function. Associations between risk and time preferences and behaviour (dietary patterns and physical activity) will be investigated. For the health economic evaluation, incremental cost-effectiveness and cost-utility ratios (ICER/IUCR: additional cost per additional LGA

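### HbA1c and four biomarkers have a value at randomisation, but section 3.2 compares them without using it: valid, yet less precise than it need be

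*Combined protocol and SAP*

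**What the plan says.** Section 2.2 states that HbA1c and the four biomarkers "will be assessed at V2 as well as at the first visit between 36+0 and 38+6 weeks of gestation", the latter being V4. Section 2.3 schedules a postpartum examination within 48 hours of delivery (VPP1) "for assessment of neonatal parameters and maternal HbA1c and glycosylated fibronectin, hsCRP, proBNP, Troponin T", and lists the same markers again at VPP2.

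Section 2.4 places randomisation at V2, by minimisation in which a "0.85 assignment probability will be used to minimize the imbalance between the groups" for gestational week at entry, previous GDM and preconceptional BMI class. Section 2.5 starts the intervention at that visit: "Patients randomized to the intervention group will be equipped with a rt-CGM sensor".

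Section 3.2 names all five markers among the continuous secondary outcomes that "will be compared by student's t-test". Rank-based inference, with the Brunner-Munzel test as the example, "will be used as an alternative in case of skewed distributed parameters". No covariate is given for them. The only adjustment named for a group comparison is the Cochran-Mantel-Haenszel method for centre, a sensitivity analysis mentioned with the binary outcomes. The section does not say which visit enters the t-test, or whether the raw value or the change from V2 is compared.

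**The concern.** The V2 value is taken at randomisation, when the sensor is only just being fitted, so it can serve as a baseline covariate. A t-test on the later value alone leaves in the error term all the between-woman variation that V2 could explain. That widens the confidence interval without making the test any safer.

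HbA1c matters most here. Section 1.2 hypothesises that rt-CGM improves maternal glycaemic control, and HbA1c is a direct laboratory measure of that, available in both arms before treatment starts. The CGM measures have no pre-randomisation value, so this argument does not extend to them.

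There is a second, smaller issue. Minimisation forces the arms to be alike on three factors. If these predict the outcome, a t-test that ignores them overstates the standard error of the difference and rejects less often than its nominal 5%.

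What is at stake is efficiency for secondary outcomes. No bias is alleged.

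**Working it through.** **Inputs from the documents.** Two-sided alpha 0.05, 80% power and 169 women per arm (section 3.1); minimisation with probability 0.85 on three factors (section 2.4); visit timing (sections 2.1 and 2.2).

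**Inputs that must be assumed.** The V2-V4 correlation r; that 169 per arm have both values; the share of outcome variance R² explained by the minimisation factors; and the distribution of those factors.

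**1. The plan's own figure.** For 13.7% against 25.8%, the mean proportion is 0.1975, and

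n = [1.960·√(2·0.1975·0.8025) + 0.842·√(0.137·0.863 + 0.258·0.742)]² / 0.121² = 168.7, rounded up to 169 per arm.

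This reproduces section 3.1. The documents give no power, SD or correlation for HbA1c or the biomarkers, so the 169 is simply carried over.

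**2. Gain from the V2 value.** With linear adjustment the residual variance is (1 − r²) times the unadjusted variance, and the confidence interval narrows by 1 − √(1 − r²). By the noncentral t distribution, the unadjusted test with 169 per arm has 80% power at 0.306 SD. The power column below is at that same difference. The equivalent size is 169/(1 − r²), the number per arm that an unadjusted test would need for the same precision.

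| r (assumed) | Variance cut | CI narrower by | Detectable difference, 80% power | Power at 0.306 SD | Equivalent n per arm |
|---|---|---|---|---|---|
| 0 | 0% | 0% | 0.306 SD | 80% | 169 |
| 0.1 | 1% | 0.5% | 0.304 SD | 80.4% | 171 |
| 0.2 | 4% | 2% | 0.299 SD | 81.6% | 176 |
| 0.3 | 9% | 5% | 0.292 SD | 84% | 186 |
| 0.5 | 25% | 13% | 0.265 SD | 90% | 225 |
| 0.7 | 49% | 29% | 0.218 SD | 97.5% | 331 |

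A simulation with simple 1:1 allocation (4,000 trials at each of r = 0.3, 0.5 and 0.7) agrees. Type I error was 4.5% to 5.0% for the t-test and 4.75% to 4.9% for the adjusted model. Power was 79%, 79% and 80% against 83%, 89% and 98%.

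**3. Plausible r.** The interval from V2 to V4 varies widely. At the short end, the latest V2 is 31+6 plus 8 days = 33+0, which is 3 weeks before 36+0. At the long end, V2 can fall at 24+0 when the run-in is omitted. V4 is the first visit in its window and visits are 12 to 16 days apart, so on schedule it falls no later than 35+6 plus 16 days = 38+1, a gap of 14 weeks 1 day. The correlation may therefore differ by marker and be low for some.

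**4. Effect of ignoring the minimisation factors.** If the factors were perfectly balanced, the variance of the t statistic under no effect would be about 1 − R². The true size of the nominal 5% test would then be 2·Φ(−1.96/√(1 − R²)): 3.9% at R² = 10% and 2.8% at R² = 20%.

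This was simulated with minimisation as planned: 6,000 trials of 338 women, gestational week in four equal levels, previous GDM in 20% and BMI classes 40/30/30%, all three distributions assumed. The t-test rejected in 4.1% and 3.1% of trials, and the model containing the factors in 5.1% and 5.2%. Repeat runs gave 3.5% to 4.1% and 2.7% to 3.1% for the t-test. With weaker factors (R² of 2% and 5%; 4,000 trials) the t-test was close to nominal, at 4.9% and 4.6%.

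**The case against.** **These are unpowered secondary outcomes and the test is valid.** True. Section 3.1 powers only LGA, and section 3.2 makes no multiplicity adjustment. That limits the importance of the point. It is no reason to leave unused a baseline value that is already collected.

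**The t-test might be meant for change from V2.** Section 3.2 does not exclude this, but it does not say it either. A change score would not close the gap: its variance factor is 2(1 − r), and 2(1 − r) − (1 − r²) = (1 − r)², which is never negative. At 0.306 SD its power is 66% at r = 0.3 and 80% at r = 0.5, against 84% and 90% with V2 as a covariate. Below r = 0.5 it does worse than the raw V4 comparison. What stands is that visit and scale are unstated and need to be fixed.

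**The plan calls itself a selection of methods.** That leaves room for further analyses, but these five outcomes are assigned a test by name. In an open-label trial, a covariate set chosen after the data are seen would be open to challenge.

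**The gains rest on assumed values.** This stands. At r of 0.1 or less the benefit is negligible, and at R² of 5% or less the conservatism hardly matters. Women who deliver before V4 have no V4 value, so 169 per arm is optimistic. When r is near zero, however, adjusting costs about one degree of freedom.

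**Adjustment brings its own choices.** This also stands. A missing V2 value needs a rule, or women drop out of an intention-to-treat comparison. A log-scale model estimates a ratio of geometric means, which is a different quantity from the one a rank test addresses. Centre is not a minimisation factor; including it is a judgement, supported by the plan's own concern about centre effects for binary outcomes. All of this can be settled in the plan's wording.

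**Conclusion.** The point holds and should be acted on. It concerns precision for five named secondary outcomes; the planned comparison is not biased, and the primary LGA test and sample size are unaffected. Under the assumed range r = 0.3 to 0.7, with 169 women per arm having both values, the adjusted analysis gives confidence intervals 5% to 29% narrower. At r = 0.5 that is worth about 56 more women per arm (225 − 169) at no extra data collection. At r near zero the two analyses are practically the same. The conservatism from ignoring the minimisation factors is secondary and depends on those factors explaining roughly 10% or more of the outcome variance.

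**What to change.** In section 3.2, before unblinding:

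- Make the main analysis of HbA1c, glycosylated fibronectin, hsCRP, proBNP and Troponin T a linear model of the V4 value on treatment, V2 value, the three minimisation factors and centre. Use the log scale for skewed markers and report the effect as a ratio of geometric means.
- Say which visit is the main one. The same model can serve VPP1 and VPP2.
- State how a missing V2 value is handled so that no randomised woman with an outcome is lost, for example by imputing the overall V2 mean.
- Keep the planned t-test or rank test as a sensitivity analysis.
- Extend the model to fetal biometry at V4. Section 2.10 says "A detailed fetal ultrasound examination will be performed at V2 and repeated at V4", so a baseline exists, and section 3.2 names no test for it.
- For continuous outcomes without a V2 value (CGM measures, newborn anthropometry, postpartum OGTT), adjust for the minimisation factors and centre. Any gain there depends on how well these predict the outcome, which the documents do not show.

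The cost is analysis-plan wording and a few lines of R. The V2 values and minimisation factors are already collected, and visits, sample size and the primary analysis stay as they are.

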## **4. General rules and provisions**

### *4.1. Ethical aspects*

The present study will be performed in accordance with the current guidelines of the Declaration of Helsinki following the criteria of Good Scientific Practice. The study protocol will be evaluated and approved by the local ethics committees. Subsequent amendments to the Protocol will be submitted to the Ethics Committee for review. All participating patients will be informed about possible complications. Their consent to participate in the study is noted by the signature (and date) on the consent form.

### *4.2. Legal regulations and provisions relevant to the study, in particular the requirements of good clinical practice (GCP), good manufacturing practice (GMP), as well as good laboratory practice (GLP), Quality assurance and Data security and Monitoring*

The principle investigators will be regularly informed about the progress of the study and will be instructed immediately in cases of problems and uncertainties. Any complication with possible connection to study participation will be declared to the Ethical Commission within 24 hours. Statistical analyses are based on the allocation of a continuously registered individual number, which is indirectly personalized and can only be decoded by the principle investigators. Every investigator is bound to secrecy. An electronic CRF will be provided by the KKS (Koordinationszentrum für Klinische Studien), the Medical University's monitoring facility. In addition, the KKS will support the project by providing, quality control, query management, data close out.

### *4.3. Data protection*

A transfer of the data, in particular to the contractual partner (Dexcom, Inc., California, USA), takes place only in encrypted or anonymous form. For any publications, only the encrypted or anonymized data will be used. The manufacturer of the medical device (Dexcom) has access to anonymised encrypted clinical data, such as glucose readings, therapy, or size and weight. As well as insight into clinical data of the study participant's child (height, weight,

Task	0	2	4	6	8	10	12	14	16	18	20	22	24	26	28	30	32	34	36
Sample Acquisition																			
Data Collection																			
Data analysis																			
Dissemination of results																			

measurements of the head, arm, forearm, thigh and calf of your child or complications at birth).

However, identification is not possible on the basis of this data.

## 5. Timeline

Gantt chart of timeline and assigned tasks in the 48 months of the project. Colors represent individual contributors of principal investigator and co-applicants. CSG (yellow); MR (blue); AT (red)

